The toxicity grading of laboratory tests is determined based on the NCI CTCAE V4.03. All AEs, adverse drug reactions and serious adverse events will be summarised by system organ class, severity and relationship to study drug.

Pharmacokinetics:

The statistical analysis of PK parameters will be performed using the validated software Phoenix® WinNonlin® version 6.3 or higher (Certara USA, Inc., Princeton, NJ) (actual version will be stated in the final report).

The individual plasma/urine concentration and pharmacokinetic parameters will be presented in listings and their descriptive statistics summarised in tables.

STUDY SYNOPSIS (cont.)

Background:

N-acetyl-L-cysteine (NAC) is the N-acetyl derivative of the naturally occurring amino acid L-cysteine. NAC was introduced into the Italian pharmaceutical market in 1965 and it is now manufactured and marketed by Zambon S.p.A. in Europe, Asia, South America, Central America, and the Middle East, under various trade names ([Ventresca 1989](#)).

NAC is widely known as a mucolytic agent, with a well-established use in the treatment of respiratory tract disorders. However, after more than 35 years from its introduction in the clinical practice, this molecule continues to be the object of scientific interest due to its potential in the treatment of several conditions other than those related to the respiratory system. NAC can also act as a direct antioxidant agent due to the -SH group ([Auroma 1988](#)) and can easily penetrate into the cells where it is deacetylated to L-cysteine, thus supporting the biosynthesis of glutathione ([Ziment 1988](#)).

Clinical pharmacology and pharmacokinetics

Several pharmacokinetic (PK) studies were carried out in healthy volunteers ([Borgstrom 1986](#), [Olsson 1988](#), [Burgunder 1989](#), [De Caro 1989](#), [Borgstrom 1990](#), [Frascio, Crestani 2002](#), [Rusca 2014](#), [Rusca 2010](#), [Rusca 2002](#)). Further PK studies were carried out in patients with chronic liver damage ([Jones 1997](#)), with liver damage caused by paracetamol overdose ([Prescott 1989](#)), in subjects under long-term treatment for chemoprevention ([Pendyala 1995](#)), in patients with respiratory disorders ([Rodenstein 1978](#)) and in patients with End Stage Renal Diseases ([Internal report 2002](#)).

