4.10.1 Adverse Events

AEs will be coded by System Organ Class (SOC) and Preferred Term (PT), using the Medical Dictionary for Regulatory Activities (MedDRA version 22.0).

AEs will be classified as pre-treatment AEs (PTAEs) and TEAEs, according to the period of occurrence, as follows:

- PTAEs: all AEs occurring before the first dose of IMP and not worsening after the first dose of IMP
- TEAEs: all AEs occurring or worsening after the first dose of IMP

Where dates are missing or partially missing, adverse events will be assumed to be treatment-emergent, unless there is clear evidence (through comparison of partial dates) to suggest that the adverse event started prior to the first dose of IMP. The detailed rules are described in [Appendix 2](#).

Individual PTAEs and TEAEs will be listed in subject data listings. No summary table will be provided for PTAEs.

Serious adverse event (SAEs) occurring or worsening after the first dose of IMP are defined as TESAEs.

For all TEAE tables, a subject will be counted only once for each System Organ Class (SOC) and each PT, even if the subject reported more than one event under each subcategory. Unless specified otherwise, TEAE tables will be ordered in terms of

decreasing number of subjects for SOC and then PT within the SOC in the column of “NAC 600 mg”, and then alphabetically for SOC and PT within the SOC if the frequency is tied.

For each subject and each adverse event, the worst severity recorded will be attributed and used in the by-severity summaries. Similarly, the worst causality (most related to treatment) will be attributed and used in the by-causality summaries. If severity or causality is missing, the worst case will be assumed.

An overview table will summarize the number and percentage on subject level of the following categories and by period (single and multiple dose):

- Any TEAE
- Any TEAE related to IMP
- Any severe TEAE
- Any severe TEAE, related to IMP
- Any TEAE with outcome of death
- Any TEAE with outcome of death, related to IMP
- Any TESAE
- Any TESAE, related to IMP
- Any TEAE leading to discontinuation of IMP
- Any TESAE leading to discontinuation of IMP
- Any TEAE leading to discontinuation of IMP, related to IMP
- Any TEAE leading to dose interruption

TEAE summaries will present the number and percentage of subjects reporting at least one TEAE. The following summaries will be provided:

- TEAEs by SOC and PT
- TEAEs by SOC and PT, by maximum severity

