- TEAEs by SOC and PT, by maximum relationship
- TEAEs related to IMP, by SOC and PT
- TESAEs by SOC and PT
- TESAEs by SOC and PT, by maximum severity
- TESAEs by SOC and PT, by maximum relationship
- TESAEs related to IMP, by SOC, PT
- TEAE leading to IMP permanently stopped, by SOC and PT
- TEAE leading to death, by SOC and PT

The number and percentage of deaths will also be summarized.

The following by-subject AE listings will be provided:

- TEAEs
- TESAEs
- TEAEs related to IMP
- TEAEs leading to drug permanently stopped
- TEAEs leading to death
- PTAEs
- Deaths

The listings will include: subject identifier, age, sex, race, adverse event (SOC, PT, and verbatim term), period, date of onset, date of resolution, duration, severity, seriousness, action taken, outcome and causality.

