	Partial	The last day of the month and the last month (i.e. December) will be used if the day/month of stop date is missing. If the imputed stop date is prior to the date of first dose of study drug, considered as prior; if the imputed stop date is on or after the date of first dose of study drug, considered as concomitant.
	Missing	Considered as concomitant.

Algorithm for Treatment-Emergent Adverse Events:

Start/ Increase Severity Date	Stop Date	Action
Known	Known	Considered as a TEAE if start/increase severity date on or after the date of the first dose of study drug.
	Partial	Considered as a TEAE if start/increase severity date on or after the date of the first dose of study drug and on or before the last dose of study drug + 30 days. The last day of the month and the last month (i.e. December) will be used if the stop day/month is missing.
	Missing	Considered as a TEAE if start/increase severity date on or after the date of the first dose of study drug and on or before the last dose of study drug + 30 days.
Partial, but known components show that it cannot be on or after first study drug taken date.	Known	Not a TEAE. The first day of the month and January will be used if the start day/month or the increase severity day/month is missing.
	Partial	Not a TEAE. The first day of the month and January will be used if the start day/month or the increase severity day/month is missing. The last day of the month and the last month (i.e. December) will be used if the stop day/month is missing.
	Missing	Not a TEAE. The first day of the month and January will be used if the start day/month or the increase severity day/month is missing.
Partial, could be on or after first study drug taken date	Known	Considered as TEAE, if stop date is after first study drug taken date. The first study drug taken date will be used if start/increase severity date is in the same month/year with first study drug taken date, or the first day of the month and January will be used if the start day/month or the increase severity day/month is after first of study drug taken date. Considered as not TEAE, if stop date is prior to first of study drug taken date. The first day of the month and January will be used if the start day/month or the increase

Start/ Increase Severity Date	Stop Date	Action
		severity day/month is missing.

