	Partial	Considered as TEAE. The first of study drug taken date will be used if start/ increase severity date is in the same month/year with first study drug taken date, or the first day of the month and January will be used if the start day/month or the increase severity day/month is after first study drug taken date. The last day of the month and the last month (i.e. December) will be used if the stop day/month is missing.
	Missing	Considered as TEAE. The first study drug taken date will be used if start/ increase severity date is in the same month/year with first study drug taken date, or the first day of the month and January will be used if the start day/month or the increase severity day/month is after first study drug taken date.
Missing	Known	Considered as TEAE if stop date is on or after the date of the first dose of study drug.
	Partial	The last day of the month and the last month (i.e. December) will be used if the stop day/month is missing. If the imputed stop date is on or after the first dose of study drug considered as a TEAE; if the year is missing, considered as a TEAE.
	Missing	Considered as a TEAE

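### SAP Appendix 2 limits treatment-emergent status to 30 days after last dose only when the start date is known and the stop date is incomplete, which contradicts the definition in SAP 4.10.1

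*SAP*

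**What the plan says.** SAP 4.10.1 sets up two classes: "AEs will be classified as pre-treatment AEs (PTAEs) and TEAEs, according to the period of occurrence". The second is open-ended: "TEAEs: all AEs occurring or worsening after the first dose of IMP". Protocol version 3.0, section 15.5, gives the same definition. For incomplete dates, SAP 4.10.1 sets a default, "Where dates are missing or partially missing, adverse events will be assumed to be treatment-emergent, unless there is clear evidence" of a start before the first dose, and refers to Appendix 2 for the detailed rules.

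The TEAE algorithm in Appendix 2 then works row by row:

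- Start known, stop known: "Considered as a TEAE if start/increase severity date on or after the date of the first dose of study drug", with nothing further.
- Start known, stop partial or missing (two rows): onset must be on or after the date of the "first dose of study drug and on or before the last dose of study drug + 30 days".
- Start partial but possibly on or after first dose: no upper limit, whatever the stop date.
- Start missing: no upper limit. Where the stop date is partial, "if the year is missing, considered as a TEAE"; where it is wholly missing, the event is also a TEAE.

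**The concern.** A stop date says nothing about whether an event began after treatment, yet in these two rows its completeness decides whether a late event counts. The same event is a TEAE once a full stop date is entered and fails the TEAE condition while it is ongoing.

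Safety is a stated objective, and the protocol synopsis promises that "All AEs, adverse drug reactions and serious adverse events will be summarised by system organ class, severity and relationship to study drug". Under Protocol 16.8, an AE arising after the final visit or early termination visit (ETV) is recorded only if the investigator judges it an adverse drug reaction. Any late event lost through these two rows would therefore be one already judged drug-related.

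**Working it through.** The plan states no figure to reproduce. The check applies the Appendix 2 rows to late onset days and compares the result with SAP 4.10.1.

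**Inputs.** SAP 4.2: Treatment Day = assessment date − first dose date + 1, so first dose is Day 1. Dosing days in the protocol synopsis are 1, 4, 5 and 6, so a subject's last dose falls on one of these. The final visit is Day 8 for completers.

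**Where the limit falls.** Last permitted onset day = last-dose day + 30. First affected onset = last-dose day + 31.

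| Last dose | Last permitted onset | First affected onset |
|---|---|---|
| Day 1 | 1 + 30 = Day 31 | Day 32 |
| Day 4 | 4 + 30 = Day 34 | Day 35 |
| Day 5 | 5 + 30 = Day 35 | Day 36 |
| Day 6 | 6 + 30 = Day 36 | Day 37 |

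For a subject dosed through Day 6, the first affected onset is 37 − 8 = 29 days after the final visit.

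**Classification, last dose on Day 6, start date known.**

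| Onset | SAP 4.10.1 | Appendix 2, stop known | Appendix 2, stop partial | Appendix 2, stop missing |
|---|---|---|---|---|
| Day 9 | TEAE | TEAE | TEAE | TEAE |
| Day 36 | TEAE | TEAE | TEAE | TEAE |
| Day 37 | TEAE | TEAE | fails TEAE condition | fails TEAE condition |
| Day 46 | TEAE | TEAE | fails TEAE condition | fails TEAE condition |

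The event that fails is not a PTAE either, because that class requires onset before the first dose and no worsening after it. If the start date of the Day 46 event were only partly known, or missing, the event would again be a TEAE even with its stop date missing. Losing information about the start thus restores the status that losing information about the stop removed.

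**Effect on the output.** After "The following by-subject AE listings will be provided", SAP 4.10.1 names seven listings: five restricted to TEAEs or serious TEAEs, one of PTAEs and one of deaths (5 + 1 + 1 = 7). A non-fatal event in neither class appears in 0 of 7, and in none of the TEAE tables.

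**The case against.** **The two rows never say that a later event is excluded.** Elsewhere Appendix 2 says outright when an event is not treatment-emergent. These rows state only when an event is one and are silent beyond the limit. On that reading the definition in 4.10.1 still governs and a Day 37 event stays a TEAE. This stands to the extent that the event is unclassified only if Appendix 2 is applied over 4.10.1. It does not remove the fault: 4.10.1 sends the reader to Appendix 2 for the operating rules, and the rows disagree with each other as well as with the body.

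**The default for incomplete dates concerns a start before the first dose, not the end of the TEAE period.** This is fair. The contradiction rests mainly on the open-ended definition and on the unlimited rows.

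**Almost nothing can fall into the gap.** Monitoring stops at the final visit/ETV and no later contact is scheduled. The half-lives quoted in Protocol 6.2 are 2.27 h and 2.6 h, so 30 days (720 h) is about 317 or 277 half-lives. This stands and keeps the point minor. The case can still arise: clinically significant final-visit findings are followed until they normalise (Protocol Table 11.1.1), and Protocol 16.8 provides for late reactions found at follow-up or reported spontaneously.

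**A 30-day limit can be a sensible choice.** It can, but a real limit on the TEAE period would apply whatever the stop date.

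**Conclusion.** Minor, and wrong as written. Appendix 2 states a rule in two rows that contradicts SAP 4.10.1, Protocol 15.5 and its own other rows. The affected record is a non-fatal reaction with a known onset or worsening more than 30 days after that subject's last dose and an incomplete stop date. That is Day 37 or later for a subject dosed through Day 6. Its absence from the tables and all seven listings assumes that Appendix 2 is applied over 4.10.1 and that the event reached the database. The expected frequency is very low; the documents give no rate and identify no such event.

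A reader might infer two stronger things that the documents do not support.

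- *That late unresolved events are unclassified in every case.* Under 4.10.1 they are TEAEs; the gap depends on which text governs.
- *That Protocol 16.8 and 16.9.1 conflict over recording late serious events.* Section 16.8 requires a late reaction to be recorded but names no place. Section 16.9.1 is the specific rule for serious events and qualifies the general instruction in 16.7. Its surrounding text turns on when the event occurred, so a serious event with onset inside the window still belongs in the eCRF. What remains is a window label that the protocol does not define.

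**What to change.** Delete the 30-day clause from the two known-start rows (stop partial, stop missing), so that Appendix 2 agrees with 4.10.1.

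The SAP revision history for version 3.1 shows that the database is already locked, and SAP section 1 assigns post-lock deviations and additional analyses to a SAP Addendum. That Addendum should list any AE with a start or worsening date more than 30 days after the subject's last dose and an incomplete stop date, classed as a TEAE under 4.10.1, or state that there is none.

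The cost is one short Addendum and one data check. If an event is found, the TEAE tables and listings that it belongs in need updating. No visit or procedure changes.

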APPENDIX 3 CTC Grading for Laboratory Parameters

Laboratory measurements will be graded using the NCI-CTCAE v4.03.

		Grade						
Analytic		Direction	Unit	0	1	2	3	4
	Hematology							
Hemoglobin	Hypo	g/L	LLN <= Value	100 <= Value < LLN	80 <= Value < 100	Value < 80		
	Hypo	g/dL	LLN <= Value	10 <= Value < LLN	8 <= Value < 10	Value < 8		
	Hypo	mmol/L	LLN <= Value	6.2 <= Value < LLN	4.9 <= Value < 6.2	Value < 4.9		
WBC	Hypo	10^9/L	LLN <= Value	3 <= Value < LLN	2 <= Value < 3	1 <= Value < 2	Value < 1	
	Hypo	/mm3	LLN <= Value	3000 <= Value < LLN	2000 <= Value < 3000	1000 <= Value < 2000	Value < 1000	
Neutrophils	Hypo	10^9/L	LLN <= Value	1.5 <= Value < LLN	1 <= Value < 1.5	0.5 <= Value < 1	Value < 0.5	
	Hypo	/mm3	LLN <= Value	1500 <= Value < LLN	1000 <= Value < 1500	500 <= Value < 1000	Value < 500	
Lymphocytes	Hypo	10^9/L	LLN <= Value	0.8 <= Value < LLN	0.5 <= Value < 0.8	0.2 <= Value < 0.5	Value < 0.2	
	Hypo	/mm3	LLN <= Value	800 <= Value < LLN	500 <= Value < 800	200 <= Value < 500	Value < 200	
	Hyper	10^9/L	Value <= ULC		4 < Value <= 20	20 < Value		
	Hyper	/mm3	Value <= ULN		4000 < Value <= 20,000	20,000 < Value		
Monocytes		NA						
Eosinophils		NA						
Basophils		NA						
Platelet count	Hypo	10^9/L	LLN <= Value	75 <= Value < LLN	50 <= Value < 75	25 <= Value < 50	Value < 25	
	Hypo	/mm3	LLN <= Value	75,000 <= Value < LLN	50,000 <= Value < 75,000	25,000 <= Value < 50,000	Value < 25,000	
	Biochemistry							
Serum creatinine		Hyper	umol/L	Value <= ULN	ULN < Value <= 1.5 < ULN	1.5 < ULN < Value <= 3 < ULN	3 < ULN < Value <= 6 < ULN	6 < ULN < Value
BUN		NA						
Alanine aminotransferase (ALT)		Hyper	U/L	Value <= ULN	ULN < Value <= 3 < ULN	3 < ULN < Value <= 5 < ULN	5 < ULN < Value <= 30 < ULN	20 < ULN < Value
Aspartate aminotransferase (AST)		Hyper	U/L	Value <= ULN	ULN < Value <= 3 < ULN	3 < ULN < Value <= 5 < ULN	5 < ULN < Value <= 30 < ULN	20 < ULN < Value
Alkaline phosphatase (ALP)		Hyper	U/L	Value <= ULN	ULN < Value <= 2.5 < ULN	2.5 < ULN < Value <= 5 < ULN	5 < ULN < Value <= 20 < ULN	20 < ULN < Value
Total bilirubin		Hyper	umol/L	Value <= ULN	ULN < Value <= 1.5 < ULN	1.5 < ULN < Value <= 3 < ULN	3 < ULN < Value <= 10 < ULN	10 < ULN < Value
Albumin		Hypo	g/L	LLN <= Value	30 <= Value < LLN	20 <= Value < 30	Value < 20	

		Grade						
Analytic		Direction	Unit	0	1	2	3	4
Sodium	Hypo	g/dL	LLN <= Value	3 <= Value < LLN	2 <= Value < 3	Value < 2		
			LLN <= Value	130 <= Value < LLN		120 <= Value < 130	Value < 120	
	Hyper	mmol/L	LLN <= Value	ULN < Value <= 150	150 < Value <= 155	155 < Value <= 160	160 < Value	
Potassium	Hypo	mmol/L	LLN <= Value	3 <= Value < LLN		2.5 <= Value < 3	Value < 2.5	
	Hyper	mmol/L	Value <= ULN	ULN < Value <= 5.5	5.5 < Value <= 6	6 < Value <= 7	7 < Value	
Chloride		NA						
	Serology							
HBV		NA						
HCV		NA						
	Urinalysis							
Urine protein	Hyper		Negative	1+	2+			
	Hyper	g/24hrs	Value <= ULN	ULN < Value < 1	1 <= Value < 3.4	3.5 < Value		
	Pregnancy test							
Pregnancy test		NA						

LLN: lower limit of normal; ULN: upper limit of normal.

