The toxicity grading of laboratory tests is determined based on the NCI CTCAE V4.03.

➤ **Vital signs**

Vital signs values will be listed and summarised by descriptive statistics.

➤ **Body weight**

Body weight values will be listed and summarised by descriptive statistics.

16 DEFINITION AND HANDLING OF AEs AND SAEs

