3.2.2 Safety Variables

Safety and general tolerability of the IMP variables include:

- Treatment-Emergent Adverse Event (TEAEs)
- Physical examinations including body weight at screening, day 3 and final visit/ETV.
- Vital signs at screening, day 1 (pre and post dose), day 3 (post dose), day 6 (pre and post dose) and Final visit (post dose)/ETV.
- 12-lead ECG at screening.

- Laboratory tests at screening, day 3 and the final visit/ETV:
 - Haematology:
Leukocytes and leukocyte differential count (percentage values and absolute values), erythrocytes, haemoglobin (conv. units), haemoglobin (IS units), haematocrit, MCV, MCH, MCHC, thrombocytes.
 - Blood chemistry:
Electrolytes: sodium, potassium, calcium, chloride, inorganic phosphorus
Enzymes: alkaline phosphatase, γ -GT, AST, ALT.
Substrates/metabolites: total bilirubin, creatinine, glucose, BUN or urea, uric acid, total cholesterol, triglycerides.
Proteins: total proteins.
 - Urine analysis:
Urine chemical analysis: pH, specific gravity, appearance, colour, nitrites, proteins, glucose, urobilinogen, bilirubin, ketones, blood, leukocytes, erythrocytes, epithelial, crystals, cylinders.

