4.10.2 Clinical Laboratory Evaluation

Laboratory values (hematology, biochemistry, and urinalysis) will be listed by subject and study time point including changes from baseline for continuous variables. The baseline for the laboratory values will be the results obtained on the last measurement before the first dose.

All values outside the clinical reference ranges will be flagged in the data listings. The abnormal values will be flagged with 'L' for values below the lower limit of the clinical reference range and 'H' for values above the upper limit of the clinical reference range and included in the listings. The Investigator will assess whether the values outside the clinical reference range are clinically significant and these will be reported as "abnormal, not clinically significant (NCS)" or "abnormal, clinically significant (CS)". Clinically significant laboratory values will be recorded by the Investigator as AEs.

Quantitative laboratory assessment reported as "<X", i.e. BQL, or ">X", i.e. above the upper limit of quantification, will be converted to X for the purpose of quantitative summaries, but will be presented as recorded, i.e. as "<X" or ">X" in the listings.

The toxicity grading of laboratory tests is determined based on the NCI CTCAE V4.03 ([Appendix 3](#)).

The following summaries will be provided for laboratory data:

- Absolute value and change from baseline for continuous data by scheduled time point.
- The number and percentage of subjects in each test result category for categorical data, by scheduled time point.
- Shifting from baseline of subjects with lab results evaluation as Normal, NCS, and CS, by scheduled time point.
- Shifting from baseline of subjects with lab results evaluated by NCI CTCAE V4.03 by toxicity grading and scheduled time point.

The following laboratory data listings will be provided:

- Listing of laboratory test results
- Listing of abnormal laboratory test results
- Listing of other lab tests and pregnancy tests.

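### SAP Appendix 3 has no row for 8 of the 17 blood-chemistry analytes measured, so those 8 cannot enter the planned CTCAE shift table, and it grades albumin, which is not measured

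*SAP*

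**What the plan says.** Protocol 15.5, under laboratory data, sets the rule: "The toxicity grading of laboratory tests is determined based on the NCI CTCAE V4.03". SAP 4.10.2 repeats it and refers the reader to Appendix 3. Appendix 3 opens with "Laboratory measurements will be graded using the NCI-CTCAE v4.03". None of these places restricts grading to a subset of tests.

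SAP 3.2.2 gives the chemistry panel in four groups:

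- four analytes in one group: "Enzymes: alkaline phosphatase, γ -GT, AST, ALT"
- five analytes in another: "Electrolytes: sodium, potassium, calcium, chloride, inorganic phosphorus"
- a single analyte in a third: "Proteins: total proteins"
- seven analytes in the largest group: "Substrates/metabolites: total bilirubin, creatinine, glucose, BUN or urea, uric acid, total cholesterol, triglycerides"

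Protocol 12.2 (version 3.0) has the same panel.

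The grades feed one of the four laboratory summaries in SAP 4.10.2: "Shifting from baseline of subjects with lab results evaluated by NCI CTCAE V4.03 by toxicity grading and scheduled time point".

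The biochemistry part of Appendix 3 has rows for creatinine, BUN, ALT, AST, ALP, total bilirubin, albumin, sodium, potassium and chloride. BUN and chloride are marked NA; the others carry limits.

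**The concern.** The grading rule covers laboratory tests in general, but its working table does not match the tests that the trial runs. Eight measured chemistry analytes have no row, and one analyte that is not measured has graded rows. This suggests a general template that was not fully fitted to this study.

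What is at stake is how the shift table will be read. A programmer following Appendix 3 has no rule for the eight analytes, so no value of any of them, however abnormal, can enter the CTCAE table. Someone who sees few or no shifts there could take that as a statement about the whole chemistry panel, when most of the panel could not have produced a shift. The table also gives no way to tell an analyte that was deliberately left ungraded from one that was forgotten.

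**Working it through.** The documents state no count of graded analytes, so there is no figure to reproduce. The check compares two lists.

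**Inputs.** Panel: SAP 3.2.2, confirmed against Protocol 12.2, with BUN or urea counted once. Rows: the biochemistry part of SAP Appendix 3.

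| Group in SAP 3.2.2 | Measured | Row with limits | Row marked NA | No row |
|---|---|---|---|---|
| Electrolytes | 5 | 2 (sodium, potassium) | 1 (chloride) | 2 (calcium, inorganic phosphorus) |
| Enzymes | 4 | 3 (ALP, AST, ALT) | 0 | 1 (gamma-GT) |
| Substrates/metabolites | 7 | 2 (total bilirubin, creatinine) | 1 (BUN) | 4 (glucose, uric acid, total cholesterol, triglycerides) |
| Proteins | 1 | 0 | 0 | 1 (total proteins) |
| Total | 17 | 7 | 2 | 8 |

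**Results.**

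- Panel: 5 + 4 + 7 + 1 = 17.
- Appendix 3 biochemistry analytes: 7 + 2 + 1 (albumin) = 10, of which 9 are in the panel.
- Panel analytes with no row: 17 − 9 = 8, and 8/17 = 47.1%.
- Panel analytes that can receive a grade: 7/17 = 41.2%.
- Panel analytes that cannot, including the two marked NA: (8 + 2)/17 = 58.8%.

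**How many grades are lost.** This depends on how many of the eight have limits in CTCAE v4.03, which the documents do not reproduce. Call that number k, with 0 ≤ k ≤ 8. A reconciled table would grade 7 + k of the 17, that is, anything from 7/17 (41.2%) to 15/17 (88.2%). The documents do not place k within this range.

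**What absence from the table means.** Appendix 3 gives an explicit NA to BUN, chloride, monocytes, eosinophils, basophils, HBV, HCV and the pregnancy test. But erythrocytes, haematocrit, MCV, MCH and MCHC are also measured under SAP 3.2.2 and have neither a row nor an NA. In urinalysis only protein has a row. A missing row is therefore ambiguous: it may be an oversight, or it may mean that no criterion applies.

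**The case against.** The strongest case on the other side is that little information is lost. Under SAP 4.10.2 every quantitative analyte, with or without a row in Appendix 3, is summarised as value and change from baseline. Results outside the reference range are flagged low or high, assessed by the investigator as clinically significant or not, listed, and carried into a Normal/NCS/CS shift table. Clinically significant values become adverse events. Protocol 15.5 adds a table of abnormal values. A marked gamma-GT rise would be visible in several places. All of this stands, and it confines the gap to CTCAE grading.

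The objection also defeats several stronger readings that a reader might be tempted to draw:

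- *Almost half of the chemistry grades are lost.* The documents do not support this, because they do not show which of the eight analytes have v4.03 limits.
- *The NA marks prove that the missing rows are errors.* They do not, because the five haematology indices also lack both a row and an NA.
- *A graded safety endpoint is incomplete.* There is no such endpoint. Laboratory parameters are a secondary variable, and the grade feeds one summary in a descriptive, single-arm study of 24 subjects.
- *Liver safety is left ungraded.* ALT, AST, ALP and total bilirubin all have limits. Exclusion criterion 3, which singles out hepatic abnormality, governs eligibility at screening and not post-dose grading.

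The albumin rows do no harm by themselves, since no albumin results are planned. They matter only as a sign that the table and the panel were not matched.

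The objection does not remove the mismatch itself. Protocol and SAP promise grading of laboratory tests without limiting it, and the table that carries out the promise says nothing about 8 of the 17 chemistry analytes.

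**Conclusion.** The point holds as a specification gap in one planned safety output. Appendix 3 has no row for 8 of 17 measured chemistry analytes (47%), has limits for only 7 (41%), and grades one analyte that is not measured. As written, the eight cannot appear in the CTCAE shift table, and that table cannot be read as covering the chemistry panel.

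The consequence is modest. The primary pharmacokinetic results are untouched, and the other laboratory reporting of these analytes is intact. The number of grades actually lost is unknown from the documents and lies between 0 and 8 analytes.

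The conclusion assumes that the PDF reading of Appendix 3 is complete. One albumin line appears to be displaced under sodium. The sequence of rows shows no visible gap, but the source file should be checked before anyone acts.

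**What to change.** 1. Confirm in the source file that the eight rows are absent from Appendix 3.
2. Reconcile Appendix 3 with SAP 3.2.2. For each measured analyte enter the CTCAE v4.03 limits where v4.03 has them, in both directions where it gives both, and an explicit NA where it has none. Treat the unlisted haematology indices and urinalysis items in the same way, so that a missing row no longer has two meanings.
3. Delete the albumin rows.
4. Re-run the CTCAE shift table and any listing that shows grades. State beneath the table which analytes are gradable.
5. Record the change in a SAP Addendum. The SAP revision history places the latest edits after database lock, and SAP section 1 sends deviations and additional analyses after lock to an addendum.

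The cost is an appendix correction and a small amount of reprogramming on existing data. No new data are needed.

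### SAP Appendix 3, as printed, gives ALT and AST between 20 and 30 x ULN two grades and dipstick protein above 2+ none; low impact, confined to the CTCAE shift table

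*SAP*

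**What the plan says.** SAP Appendix 3 opens by naming its standard: "Laboratory measurements will be graded using the NCI-CTCAE v4.03". It then lists bounds for Grades 0 to 4, row by row. SAP 4.10.2 uses those grades in one planned summary: "Shifting from baseline of subjects with lab results evaluated by NCI CTCAE V4.03 by toxicity grading and scheduled time point".

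The rows at issue are:

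- **ALT and AST.** In both rows Grade 3 is "5 < ULN < Value <= 30 < ULN" and Grade 4 is "20 < ULN < Value". The alkaline phosphatase row has the same Grade 4 cell, but its Grade 3 cell is "5 < ULN < Value <= 20 < ULN".
- **"Urine protein".** One row is semi-quantitative: negative is Grade 0, 1+ is Grade 1, 2+ is Grade 2, and the last two cells are blank. A second row, in g/24hrs, ends Grade 2 below 3.4 and starts Grade 3 above 3.5.
- **Lymphocytes, Hyper.** Grade 0 runs up to the upper limit, Grade 1 is blank, Grade 2 runs from above 4 to 20 x 10^9/L, and Grade 3 is above 20. A second row repeats this per mm3.
- **Sodium, Hyper.** The Grade 0 cell is bounded by LLN from below and has no upper bound.

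The footnote defines the limits ("LLN: lower limit of normal; ULN: upper limit of normal") but gives no laboratory values for them.

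**The concern.** A grading table has to send every possible result to exactly one grade. If a result meets two grades, the order of the programmer's conditions decides the tabulated grade. If it meets none, the result is missing from the table. For ALT and AST the ambiguity lies between Grades 3 and 4, so ascending if/else code would return the lower grade. For dipstick protein the ungraded results lie above the highest listed level. Either way, the planned shift table cannot be reproduced unambiguously from the SAP as printed.

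**Working it through.** The plan states no figure to reproduce here. The check codes each row as printed, reading '5 < ULN' as 5 x ULN, and lists every grade that a test value satisfies.

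**ALT and AST** (Grade 3: above 5 to 30 x ULN; Grade 4: above 20 x ULN), against ALP (Grade 3: above 5 to 20; Grade 4: above 20):

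| Value (x ULN) | ALT/AST as printed | ALP as printed | ALT/AST with Grade 3 ending at 20 |
|---|---|---|---|
| 20 | 3 | 3 | 3 |
| 20.1 | 3 and 4 | 4 | 4 |
| 25 | 3 and 4 | 4 | 4 |
| 30 | 3 and 4 | 4 | 4 |
| 30.1 | 4 | 4 | 4 |

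The overlap is 30 - 20 = 10 x ULN wide in each row. The other rows built on multiples of ULN meet cleanly: creatinine at 1.5, 3 and 6; ALP at 2.5, 5 and 20; bilirubin at 1.5, 3 and 10.

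**Urine protein.** Negative, 1+ and 2+ give Grades 0, 1 and 2. A 3+ result gives no grade. The same would hold for trace or 4+ if the laboratory reports them, which the documents do not say. The g/24hrs row cannot fill in. Protein is measured only within routine urinalysis (protocol 12.2, SAP 3.2.2), and timed urine is collected only for NAC pharmacokinetics (protocol 12.3.2). That row also leaves 3.4 to 3.5 inclusive ungraded, which is moot while it is unused.

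**Lymphocytes, Hyper.** The laboratory ULN is not given, so it is an assumption, shown over 3.0 to 5.0 x 10^9/L. One Grade 0 cell prints ULC, which the abbreviation list does not define; it is read here as ULN.

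| Assumed ULN | Gap, 4 - ULN | Overlap of Grades 0 and 2, ULN - 4 |
|---|---|---|
| 3.0 | 1.0 | none |
| 3.2 | 0.8 | none |
| 3.5 | 0.5 | none |
| 4.0 | none | none |
| 4.5 | none | 0.5 |
| 5.0 | none | 1.0 |

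Counts above 20 get Grade 3 alone at every assumed ULN.

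**Sodium, Hyper.** With an assumed LLN of 135 and ULN of 145 mmol/L, 148 meets Grades 0 and 1, 152 meets 0 and 2, 158 meets 0 and 3, and 162 meets 0 and 4. The overlap follows from the missing upper bound, whatever the limits are.

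**Reach.** Laboratory tests are scheduled at screening, day 3 and the final visit (SAP 3.2.2), so there are at most 24 x 2 = 48 scheduled post-dose values per analyte.

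**The case against.** The strongest objection is that the 30 may be a misreading. These cells are visibly damaged in the text available for review: the multiplication sign appears as '<', and a sodium label sits beside g/dL bounds that look like albumin's. If the page prints 20, the ALT and AST point disappears. That caution stands, but 30 appears in two separate rows while the ALP row reads 20, so a misread is unlikely.

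The second objection is that little would be lost. SAP 4.10.2 also plans absolute values and changes from baseline, counts by result category (where a 3+ protein would show), a shift across normal, NCS and CS, and listings of all and of abnormal results. It adds that "All values outside the clinical reference ranges will be flagged in the data listings", and clinically significant values are recorded as AEs. Protocol 10.3 excludes clinically significant hepatic abnormality above 3 times the upper limit. All of this stands and is why the impact is low. It does not make the printed rule correct.

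A reader might infer that the table misfiles or drops the worst values in general. The documents do not support that. ALT and AST above 30 x ULN are Grade 4 only, and between 20 and 30 misfiling depends on a coding order that the SAP does not give. Lymphocyte counts above 20 are graded without ambiguity; the fault there lies near the upper limit, and its form depends on the laboratory ULN. Nor can one say what share of dipstick levels is ungraded, because the reporting scale is not stated.

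**Conclusion.** Appendix 3 is wrong as written, with low impact. Subject to checking the 30 at source, ALT and AST above 20 and up to 30 x ULN meet two grades with no rule to choose between them. Dipstick protein above 2+ has no grade and no usable substitute row. The raised-lymphocyte rows work throughout only at a ULN of exactly 4.0 x 10^9/L: below that there is a gap, above it an overlap of Grades 0 and 2. The raised-sodium rows overlap with Grade 0, again subject to checking the printed cell.

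The effect is confined to the CTCAE shift table. One affected subject would be 1/24 = 4.2% of the planned sample, which shows scale only; the documents give no basis for how often such values would occur. Nor do they show that any subject fell in these bands or that any output was wrong.

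**What to change.** 1. Check the ALT, AST and sodium cells on the source page.
2. End ALT and AST Grade 3 at 20 x ULN, matching their own Grade 4 lower bound and the ALP row.
3. Make the top dipstick category 2+ or more, or give 3+ another grade, after checking the declared NCI-CTCAE v4.03. Settle trace in the same way if it is reported.
4. Make the lymphocyte Hyper Grade 0 and Grade 2 bounds meet whatever the ULN, in both unit rows. A single cut at 4, or a cut at the larger of ULN and 4, would each do this; confirm the choice against the standard. Merely assigning ULN to 4 to Grade 0 would leave the overlap when the ULN exceeds 4.
5. Give sodium Hyper Grade 0 an upper bound at ULN.
6. Delete the g/24hrs row.
7. Confirm that the programmed grades follow the corrected table, and check whether any value falls in the affected bands.

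The cost is about six cells (ALT, AST, dipstick protein, two lymphocyte rows, sodium), one deleted row and a program check. The revision history shows that this appendix was last edited after database lock, so any change belongs in a SAP addendum, as SAP section 1 provides.
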